2. BACKGROUND INFORMATION AND SCIENTIFIC RATIONALE

2.1 Disease Background

SLE is a chronic autoimmune disease characterized on a molecular level by pathogenic autoantibodies against nuclear antigens such as ds-DNA. Clinically, it is a disease characterized by recurrent flares that may involve any organ system and anti-dsDNA antibodies are associated with disease flares and severity, especially with active nephritis [5-7]. Anti-dsDNA antibodies are known to stimulate inflammatory responses through several mechanisms including immune complex formation with subsequent Fc receptor activation, TLR activation and complement activation. Additionally, direct binding of anti-dsDNA antibodies may modulate cell function or gene expression through Fc independent and dependent mechanisms. Pertinent to this clinical trial, a subset of anti-dsDNA antibodies that are cross-reactive with the DWEYS pentapeptide have been shown to bind to NMDA (N-methyl-d-aspartate) receptors found in neurons, leading to regional neuronal dysfunction and/or death and subsequent behavioral changes in mice [1, 8]. These same autoantibodies also cross react with glomerular antigens leading to tissue damage [9]. Inhibition of these parameters (tissue binding, immune complex formation, TLR stimulation) may lead to amelioration of the disease.

Many cells are involved in SLE pathogenesis; the principal players are thought to be B cells, T cells and dendritic cells. Monocytes are heterogenous circulating blood cells that make up approximately 10% of human peripheral blood leukocyte population. They rapidly mobilize to

sites of inflammation where inflammatory molecules initiate their differentiation into macrophages or dendritic cells [10]. The half life of a monocyte in circulation is approximately 72 hours [11]. This relatively short half life allows for a continuous repopulation of dendritic cells and macrophages. It may also allow for a rapid determination of potential immunomodulatory effects of certain drug therapies. Plasmacytoid dendritic cells (pDCs) are the main producers of interferon alpha ($IFN\alpha$), an important cytokine involved in the pathogenesis of lupus [12-13]. $IFN\alpha$ stimulates dendritic cell maturation, which in turn promotes loss of tolerance and activation of autoreactive T and B lymphocytes, production of autoantibodies and immune complexes, and further production of $IFN\alpha$.

High mobility group box protein 1 (HMGB1) is one of a group of highly conserved, ubiquitous, nuclear non-histone proteins, previously known as DNA-binding proteins, involved in the maintenance of nucleosome structure and regulation of gene expression. More recently, extracellular HMGB1 has been identified as a potent pro-inflammatory cytokine that is increased in serum and tissue during infection and inflammatory processes (reviewed in [14-15]). Large amounts of HMGB1 are released by a variety of tissue-specific cells as well as activated monocytes and macrophages in response to endotoxin or other inflammatory cytokines such as $IL-1\beta$, $TNF\alpha$ and $IFN\gamma$. HMGB1 released by apoptotic and necrotic cells also contributes to the extracellular pool. The pro-inflammatory effects of extracellular HMGB1 are mediated by cell surface receptors RAGE (Receptor for Advanced Glycation End Products), TLR 2, TLR4 and the intracellular TLR9 receptor. Engagement of any of these receptors leads to $NF-\kappa B$ activation via different intracellular signaling pathways thereby initiating and perpetuating the release of pro-inflammatory cytokines. There is also enhancement of DC maturation and resulting increased production of $IFN\alpha$. High levels of extracellular HMGB1 have been associated with infection, particularly sepsis, and other diseases characterized by sterile inflammatory responses such as rheumatoid arthritis, Sjogrens and SLE [16-18]. Pertinent to our proposed study, serum HMGB1 levels are higher in SLE patients compared to healthy controls and levels correlate with disease activity and anti-dsDNA levels and inversely with serum C3 [19]. Molecules that bind to HMGB1 and prevent these proteins from binding to their targets may serve as potential therapeutics.

There are increasing data suggesting that, in addition to their anti-retroviral activity, PIs have immunomodulatory effects on macrophage, T cell and dendritic cell function [20-24]. PIs have been shown to inhibit TLR 2 and 4 activation resulting in decreased cytokine release from peripheral blood mononuclear cells in HIV patients and serum levels of inflammatory cytokines, such as $TNF\alpha$ and $IL-6$, are decreased in patients taking PIs [20]. Immunomodulatory effects of PIs have also been demonstrated in the murine model of experimental autoimmune encephalitis where administration of ritonavir decreased mononuclear cell infiltrate and inflammatory response [25]. Anti-retroviral drugs have been shown to prevent the sterile myocarditis induced by the intracellular accumulation of retroelement ssDNA in *Trex-1* deficient mice; the animal model of human Aicardi-Goutières syndrome [26]. SLE is also associated with a genetic deficiency of *Trex-1* [27]. The ability of PIs to inhibit differentiation and maturation of DCs, accompanied by reduced secretion of inflammatory cytokines in response to TLR stimulation [21, 28], is particularly significant for SLE. $IFN\alpha$, secreted by pDCs, has been linked to disease pathogenesis as well as disease activity [12-13]. These results have led us to hypothesize that one or more of the protease inhibitors may ameliorate the effects of SLE through its effects on

multiple cells involved in the aberrant inflammatory response associated with SLE. Additionally, based on results of studies done in our lab (section 2.3) we hypothesize that PIs may also alter anti-dsDNA antibody binding to its antigens (immune complexes, tissue antigens, C1q) or through an interaction with HMGB1, displacing DNA and/or preventing ligation with intra or extracellular receptors. In particular, prevention of HMGB1 binding to TLR 9 may decrease pDC maturation, differentiation and expression of IFN α .

2.2 Significance for Lupus treatment

The current management of patients with SLE is stratified by the degree of internal organ involvement; some therapeutic agents are used for mild to moderate disease with non-major organ involvement and others for severe disease associated with major organ involvement (renal and central nervous system). Non-steroidal anti-inflammatory drugs (NSAIDs), antimalarials and glucocorticoids are generally used in the treatment of SLE without major organ involvement. Although these agents are widely used, there are only a few randomized controlled trials that demonstrate their efficacy in SLE. In addition, although studies show clinical improvement on these agents, it is clear that many patients continue to have residual disease activity (Tassiulas, I.O in Kelley's textbook of Rheum). Long term use of glucocorticoids contributes to significant toxicity such as continued immune suppression with increased risk of infection, osteoporosis, avascular necrosis, glaucoma, hypertension, hyperlipidemia, obesity and diabetes. Patients with moderate to severe and refractory disease are usually treated with more potent cytotoxic agents that suppress the immune system in a non-specific manner and have significant side effects. Cyclophosphamide, methotrexate and azathioprine, all synthetic antineoplastic drugs, and mycophenolate mofetil (MMF) are used to control disease activity and treat lupus manifestations with the potential of resulting in end organ failure. Use of these agents is associated with multiple side effects including myelosuppression, infection, hemorrhagic cystitis, malignancy, and infertility (associated with use of cyclophosphamide).

Hydroxychloroquine is an antimalarial drug that, in addition to its antimicrobial properties, has also been recognized for its immunomodulatory effects [29-30]. It has been shown to be beneficial in the treatment of rheumatologic diseases such as SLE and rheumatoid arthritis. Proposed anti-inflammatory mechanisms of hydroxychloroquine include the disruption of lysosomal acidification with resultant inhibitory effects on cell signaling, protein production and secretion, eventually leading to a decrease in proinflammatory cytokine production (particularly IL-1, IL-6, TNF α , and IFN gamma) [29]. Hydroxychloroquine also has inhibitory effects on antigen receptor signaling in B and T lymphocytes, and antigen presentation. Most recently, hydroxychloroquine was found to inhibit activation of intracellular and cell surface TLRs [31-32]. Intracellular TLRs (in particular TLR 7, 8, and especially TLR 9) are important in as SLE as these receptors bind to host nucleic acids and nucleic acid containing immune complexes leading to enhanced production of IFN α with subsequent activation of B lymphocytes, T lymphocytes and dendritic cells. The effect of hydroxychloroquine on endosome acidification inhibits the binding of nucleic acids to intracellular TLRs. A similar mechanism of action may account for inhibitory properties of novel drug therapeutics such as PIs.

Management of active SLE frequently requires the use of multiple immunosuppressive and cytotoxic drugs. Almost all of these medications are unapproved and are used off-label; their use

has become “standard of care” by the rheumatologic community as they are often efficacious for the treatment of active disease. However, these immunosuppressive and cytotoxic medications are associated with multiple toxicities and their often have limited efficacy. Thus, therapies for SLE that are more selective and associated with a safer toxicity profile are urgently needed. We are therefore interested in testing drugs that have a known immunologic effect and that are known to be relatively safe in humans.

2.3 Summary of Pre-Clinical Studies

Previous studies have shown that a specific pentapeptide sequence, DWEYS, acts as a DNA mimotope and inhibits the binding of monoclonal anti-dsDNA antibodies, R4A (a murine monoclonal anti-dsDNA antibody) and G11 (a human monoclonal anti-dsDNA antibody) to DNA, DWEYS peptide and to mouse glomeruli by occupying the antigen-binding site of these antibodies [9]. The peptide sequence is also present in the NR2A and NR2B subunits of mouse and human NMDA receptors that are found on neurons throughout the brain and DWEYS peptide inhibits binding of the R4A antibody to neurons in the brain [1, 9]. The DWEYS peptide has also been shown to inhibit transfer of the IFN signature by sera from lupus patients *in vitro* to normal peripheral blood monocytes (PBMCs) (unpublished data). The IFN signature is comprised of a set of genes that are expressed following exposure to α IFN. The importance of α IFN in lupus pathogenesis has been well-established as lupus patients are found to have a pattern of increased expression of IFN-inducible genes [33].

The DWEYS peptide shares a structural motif with protease inhibitors and *in vitro* ELISA studies have demonstrated that some of the protease inhibitors, including nelfinavir, can inhibit binding of the R4A dsDNA antibody to the DWEYS peptide and DNA in a dose dependent manner (unpublished data)(Figure 1). The structural features of the DWEYS peptide were used to design a novel peptidomimetic molecule, FISLE-412, that has been shown to neutralize anti-dsDNA/DWEYS autoantibody binding to DNA both *in vitro* and *in vivo* in a murine lupus model [3]. The protease inhibitors inhibited binding of R4A to DNA and DWEYS peptide in a manner similar to that demonstrated by the peptidomimetic molecule, FISLE-412 (Figures 1 and 2a). Nelfinavir has also been shown to block renal deposition of the R4A antibody in the glomerular binding assay (unpublished data) (Figure 2b). Similarly, nelfinavir and other PIs block the neuronal apoptosis that occurs as a consequence of anti-dsDNA antibody binding to NMDAR on neurons in the brain (unpublished data) (Figure 2c). Measurement of anti-dsDNA binding in sera from four lupus patients with active disease and elevated titers of anti-dsDNA antibodies was decreased after pre-incubation with nelfinavir *in vitro* (unpublished data)(Figure 3). These data support our hypothesis that nelfinavir may alter anti-dsDNA antibody binding *in vivo*, thereby preventing the pro-inflammatory consequences of anti-dsDNA antibody binding. Additional potential anti-inflammatory effects of nelfinavir are the decreased cytokine expression in stimulated PBMC (Figure 4). While the peptidomimetic molecule, FISLE-412, is undergoing development as a potential therapeutic agent, we anticipate that this clinical trial will demonstrate the biologic efficacy *in vivo* of nelfinavir, a protease inhibitor acting as a decoy antigen for anti-dsDNA antibodies in SLE. The re-purposing of an FDA-approved medication that has a strong safety profile for an alternate use will allow for rapid transition to the clinic for a disease in great need of novel therapeutic strategies.

[figure not shown]

3. STUDY DRUG INFORMATION

3.1 Rationale for use of study drug (nelfinavir)

As demonstrated in Figure 1, several of the PIs inhibit anti-dsDNA antibody binding to DNA and DWEYS peptide. Our decision to use nelfinavir for this clinical trial was based on an extensive review of potential drug toxicities. Nelfinavir was specifically chosen for its relatively safe profile in comparison to the other PIs and we hypothesize that nelfinavir will be well tolerated in stable SLE patients. We have employed an open-label trial with no placebo arm for the following primary reasons: (i) nelfinavir is safe and well-tolerated in HIV patients, (ii) after excluding subjects taking contraindicated medications, we have no reason to think that those enrolled will be at increased risk for toxicity to nelfinavir, (iii) we are dosing at or below the recommended dose of nelfinavir in HIV patients, (iv) we have carefully pre-determined stopping rules for toxicity, and (v) as an added immediate safety precaution, we will enroll the first four subjects sequentially with a 2 wk observation delay prior to enrolling the next subject.

3.2 Drug Description

Nelfinavir, the brand name is Viracept, is an inhibitor of the human immunodeficiency virus (HIV) protease. It is currently licensed as an antiviral medication, in conjunction with other protease inhibitors, for the treatment of HIV infection. Protease inhibition prevents the cleaving of the *gag* and *gag-pol* polyprotein and this in turn leads to the production of non-infectious viruses. Nelfinavir is [3S[2(2S*, 3S*), 3 α ,4 $\alpha\beta$,8 $\alpha\gamma$]]-N-(1,1-dimethylethyl)decahydro-2-[2-hydroxy-3-[(3-hydroxy-2-methylbenzoyl)amino]-4-(phenylthio)butyl]-3-isoquinoline carboxamide monomethanesulfonate and has a molecular weight of 663.90 (567.79 as the free base). Nelfinavir is a white amorphous powder, slightly soluble in water at pH < 4 and is freely

soluble in methanol, ethanol, 2-propanol and propylene glycol. Tablets are available for oral administration as a light blue, capsule-shaped tablet with a clear film coating in 250 mg strength (as nelfinavir free base) and as a white oval tablet with a clear film coating in 625 mg strength (as nelfinavir free base). Each tablet contains the following common inactive ingredients: calcium silicate, crospovidone, magnesium stearate, hypromellose, and triacetin. The 250 mg tablet contains FD&C blue #2 powder and the 625 mg tablet contains colloidal silicon dioxide. Nelfinavir oral powder is available for oral administration in a 50 mg/g strength (as nelfinavir free base) in bottles. The oral powder contains the following inactive ingredients: microcrystalline cellulose, maltodextrin, dibasic potassium phosphate, crospovidone, hypromellose, aspartame, sucrose palmitate, and natural and artificial flavor. Nelfinavir has a plasma half life of approximately 3.5 to 5 hours and a steady state of the drug is achieved in 6 days [34-35]. It is metabolized by several cytochrome P-450 enzymes including CYP3A4, CYP2C19, CYP2C9, and CYP2D6. The recommended nelfinavir dose for treating adults with HIV or AIDS is 1250 mg (either five 250 mg tablets or two 625 mg tablets) twice daily or 750 mg (three 250 mg tablets) three times daily (Viracept Prescribing Information. Agouron Pharmaceuticals Inc, 2008). The research pharmacy at North Shore/LIJ Health System will obtain approved drug, nelfinavir/viracept, from Alexion Pharmaceuticals ([name]) through their specialty pharmaceutical distributor, Cardinal Health ([name]) The research pharmacy at North Shore/LIJ Health System will act as the central pharmacy for all sites in the study. As such, the central pharmacy will store the study drug and dispense drug to all participating sites as needed. Once a subject has been screened for the study, the site coordinator will contact the central study coordinator at the FIMR and an adequate amount of drug for that subject to complete the study will be shipped overnight from the central pharmacy to that site so that enrollment is not delayed. Unused or expired drug will be destroyed either at the local participating site or in the central pharmacy. Details for drug storage, maintenance and disposal specifications can be found in the Manual of Procedures.

4. KNOWN AND POTENTIAL RISKS and BENEFITS

Nelfinavir is classified as an FDA Pregnancy Category B drug; there is no evidence of human risk in controlled studies. Nelfinavir crosses the placenta and no increased risk of overall birth defects following first trimester exposure in humans has been reported to the antiretroviral pregnancy registry. Nelfinavir is recommended for use in HIV positive women for prophylaxis of perinatal transmission if alternative regimens are not tolerated. Because of drug metabolism via the cytochrome p-450 enzymes, there are multiple potential interactions between Nelfinavir and other drugs. More specifically, nelfinavir inhibits cytochrome P450 3A (CYP3A) and therefore may affect serum levels of the following: benzodiazepines, anti-arrhythmics, calcium channel blockers, oral contraceptives, statins, among others (major interactions are listed in Table 1). To reduce potential toxicity, we plan to exclude subjects that are taking medications metabolized by the cytochrome P450 system and that have major interactions with nelfinavir. In addition, there are no known interactions between the immunosuppressive medications commonly used for treatment of SLE, hydroxychloroquine, corticosteroids, azathioprine, MMF, methotrexate, cyclophosphamide, and nelfinavir. There are no reasons to think lupus subjects would be more susceptible to toxicities associated with nelfinavir than individuals with HIV disease. Due to the frequency of reports of hyperglycemia attributed to nelfinavir in the post-marketing period, all subjects will be counseled to look for symptoms of hyperglycemia (increased thirst, increased hunger, frequent urination and weight loss). They will be asked about these symptoms at all of the study visits following dosing with the study drug and serum glucose will be measured on Days 14, 28, 56 and 84 so it is unlikely that nelfinavir-induced hyperglycemia would be missed.

Table 1: Major interaction between Nelfinavir and drug classes with likely adverse effect

Drug Class	Example of Drug	Possible adverse event
Antiarrhythmics	Amiodarone, Quinidine	Cardiac arrhythmias
Sedative/Hypnotic	Midazolam, Triazolam	Prolonged sedation/respirator depression
Ergot Derivative	Ergotamine, Dihydroergotamine, methylergonovine	Ergot toxicity: extremity vasospasm/ischemia
Neuroleptic	Pimozide	Cardiac arrhythmias
Proton Pump Inhibitor	Omeprazole	Decreased level/effect of nelfinavir
HMG-CoA reductase inhibitors	Lovastatin, Simvastatin	Risk of Myopathy/Rhabdomyolysis
Antimicrobial	Rifampin	Decreased drug effect
Herbal Product	St. John's wort	Decreased Drug effect

Alpha 1-adrenoreceptor antagonist	Aluzosin	Increased drug effect: hypotension
GI Motility Agent	Cisapride	Cardiac arrhythmias
PDE5 Inhibitors	Sildenafil (Revatio)	Visual disturbances, hypotension, prolonged erection, and syncope

Adapted from Package Insert 4/2012

4.2 Benefits

We anticipate that, based on their reported immunomodulatory effects and the preliminary data from our lab on anti-dsDNA antibody binding, nelfinavir may modulate inflammatory responses in SLE thereby decreasing disease activity.

5. METHODS

5.1 Design

This clinical trial is designed to assess the effect of nelfinavir on dsDNA binding in SLE patients with mild to moderate disease activity defined as follows:

[figure not shown]
- a minimum SELENA SLEDAI score of 2 (excluding points for anti-dsDNA antibodies and complement)
- no renal or nervous system disease activity
- no BILAG A criteria
- no expectation by the investigator that corticosteroids will need to be added or doses increased during the trial period
- no expectation by the investigator that immunosuppressive medication will need to be added or doses increased during the trial period

The Simon Two-Stage trial design limits exposure to study drug that is not effective and we believe that this trial design provides an efficient method for assessment of an FDA approved medication for HIV disease for another purpose. This study design does not have a placebo arm; all subjects will be dosed with nelfinavir 750 mg orally thrice daily. If the thrice daily dose is not tolerated, subjects will be allowed to decrease the dose to twice daily. For both stages of the trial the dosing period is 8 weeks followed by a 4 week observation period. A maximum of 13 subjects will be enrolled in the first stage of the trial followed by a maximum enrollment of an additional 30 in the second stage. The primary endpoint or "Response" is defined as a $\geq 35\%$ reduction in serum anti-dsDNA antibody titer from baseline values to end of treatment (8 weeks). This definition is based on established changes in anti-dsDNA titers in other lupus trials. We will test the null hypothesis that the true objective Response rate is $\leq 20\%$ (Inadequate Response Rate, which would not be clinically meaningful) versus the alternative hypothesis that the true Response rate is $\geq 40\%$ (Desirable Target Response Rate, Figure 5). Importantly, these Response Rates are consistent with results from other lupus clinical trials (e.g., immunosuppressives, steroids) where $\leq 20\%$ was considered not significant and $\geq 40\%$ was clinically meaningful. With a significance level of 0.05 and a power of 0.80, a maximum of 43 evaluable subjects (13 in Stage 1 plus 30 in Stage 2) will be required to assess the objective Response rate (Figure 5) [4]. From among the 13 subjects enrolled in Stage 1; if 3 or fewer objective Responses are observed, then the trial will be terminated (Figure 5A). If 4 or more objective Responses are observed in the first 13 subjects, however, the study will be expanded to enroll an additional 30 patients (Stage 2; Figure 5B). At the end of the study, if 13 or more Responses are observed, then the null hypothesis that the true response probability is $\leq 20\%$ will

be rejected and further investigation of nelfinavir in this patient population is warranted (Figure 5B) [4].

Treatment will be 750 mg nelfinavir thrice daily dosing (*t.i.d.*), if a given subject cannot tolerate this dose (*e.g.*, due to nausea), we will allow a step down to twice daily dosing (*b.i.d.*). Subjects and/or their insurance companies will not be charged for the nelfinavir; the study medication will be provided to all subjects free of charge. Compliance will be monitored by pill count – all evaluable subjects must maintain $\geq 80\%$ compliant (*i.e.*, ≥ 135 of 168 pills). While study endpoints will be determined immediately following treatment (8wk), durability will be assessed after a 4 week follow-up period. Because a Simon Two-Stage trial contains no placebo arm, we will be especially vigilant regarding safety. The Safety Officer and NIAMS have ultimate authority to address safety but we have incorporated clear stopping rules into the trial design (see section 5.4.2 for details).

**Figure 5. Study Design Flow Diagram
Simon Two-Stage: Nelfinavir in SLE (max 43 subjects)**

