NSAIDS and Tylenol should be held overnight or for 12 hours prior to the assessments on Day 1. The following assessments will take place on Day 1 prior to dosing with the study medication for those subjects who meet eligibility criteria *and are returning for the Day 1 visit more than 10 days after the screening visit:*

- Medical history
- Adverse event review
- Physical exam
- Medication review
- For women of childbearing potential a urine pregnancy test must be negative prior to dosing with study medication
- Laboratory assessments prior to dosing with study medication
 - **Local Laboratory** (at the participating site)
 - CBC with differential
 - Comprehensive chemistry, amylase, lipase
 - C3, C4
 - Urinalysis with micro
 - **Central Laboratory** (see **MOOP Appendix E** for processing, storage and shipping instructions)
 - anti-dsDNA and anti-DNA/DWEYS antibody titers,
 - antibodies to Sm, RNP, Ro, La, anticardiolipin antibodies: IgG, IgA, IgM
 - cytokine levels
 - interferon signature
 - CRP
- Disease activity assessments:
 - SELENA SLEDAI
 - BILAG
 - Joint count
 - PGA
 - SLICC Damage Index
- Patient Assessments:
 - LupusPRO
 - Patient global assessment (PtGA)

- Dispense 30 days of study drug, nelfinavir

For subjects that meet eligibility criteria returning for the Day 1 visit *within 10 days of the screening visit*, the SELENA SLEDAI assessment obtained at screening should be used as the Day 1 SELENA SLEDAI and a repeat CBC, comprehensive chemistry, C3, C4 and urinalysis with micro will not be performed. The following assessments will be performed for these subjects at the Day 1 visit prior to dosing with the study medication:

- Medical history
- Adverse event review
- Physical exam
- Medication review
- For women of childbearing potential a urine pregnancy test must be negative prior to dosing with study medication
- Disease activity assessments:
 - BILAG
 - Joint count
 - PGA
 - SLICC Damage Index
- Patient Assessments:
 - LupusPRO
 - Patient global assessment (PtGA)
- Laboratory assessments prior to dosing with study medication
 - **Central Laboratory** (see MOOP Appendix E for processing, storage and shipping instructions)
 - anti-dsDNA and anti-DNA/DWEYS antibody titers,
 - antibodies to Sm, RNP, Ro, La, anticardiolipin antibodies: IgG, IgA, IgM
 - cytokine levels
 - interferon signature
 - CRP
- Dispense 30 days of study drug, nelfinavir

Day 7: All subjects will return on Day 7 for the following assessments:

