- Medical history, including assessment of nelfinavir tolerability
- Adverse event review
- Physical exam
- Medication review (including a pill count for study drug; nelfinavir)
- Hyperglycemia assessment: Subjects will be asked about symptoms of hyperglycemia: increased thirst, increased hunger, frequent urination and weight loss. If symptoms are present, a serum glucose (using a fingerstick measurement or a chem-7 measurement) should be obtained. Based on the serum glucose level, the following guidelines should be followed:
 - Grade 1 or 2 Hyperglycemia (serum glucose < 250)
 - In subjects with pre-existing diabetes: these subjects can be allowed to continue in the study with intensification of their diabetes regimen and glucose monitoring

- In subjects with no history of hyperglycemia or diagnosis of diabetes: these subjects should be taken off the study medication and discontinued from the study (section 6.1.1).
- Grade 3 hyperglycemia (serum glucose > 250): subjects should be taken off study medication, discontinued from the study (section 6.1.1), treated and followed for resolution of the hyperglycemia.

Day 14: Subjects will be asked to fast after midnight the night prior to this visit. All subjects will return on Day 14 for the following assessments:

- Medical history, including assessment of nelfinavir tolerability
- Adverse event review
- Physical exam
- Medication review (including a pill count for study drug; nelfinavir)
- Hyperglycemia assessment: Subjects will be asked about symptoms of hyperglycemia: increased thirst, increased hunger, frequent urination and weight loss. If symptoms are present, a serum glucose (using a fingerstick measurement or a chem-7 measurement) should be obtained. Based on the serum glucose level, the following guidelines should be followed:
 - Grade 1 or 2 Hyperglycemia (serum glucose < 250)
 - In subjects with pre-existing diabetes: these subjects can be allowed to continue in the study with intensification of their diabetes regimen and glucose monitoring
 - In subjects with no history of hyperglycemia or diagnosis of diabetes: these subjects should be taken off the study medication and discontinued from the study (section 6.1.1).
 - Grade 3 hyperglycemia (serum glucose > 250): subjects should be taken off study medication, discontinued from the study (section 6.1.1), treated and followed for resolution of the hyperglycemia.
- Laboratory assessments
 - **Local Laboratory** (at the participating site)

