7.1.1 Handling of Dropouts and Non-Evaluable Subjects

For the evaluation of efficacy using the Simon Two-Stage Optimal Design rule, any subject who is not evaluable or drops out from the study for any reason (including adverse events), will be replaced by a new subject. The subject being replaced will not be used in the analysis of efficacy. As noted elsewhere in this protocol, a subject will be considered “evaluable” for efficacy if he/she has complied with at least 80% of the prescribed medication dosing over the entire 56 days of medication administration ($<80\%$ is “not evaluable”). This “per protocol” rule has been implemented since this is a Phase II efficacy trial and the “intention-to-treat” principle does not apply. In order to account for a standard dropout rate of 20%, the potential maximum number of subjects to be enrolled will increase to 51 subjects.

For the evaluation of safety, any subject who is exposed to at least one dose of the medication will be included in all analyses of adverse events, even if this subject is replaced under the efficacy rule cited above.

The statistical analysis for the primary endpoint, therefore, is a straightforward calculation of percent change within each subject in anti-dsDNA antibody titer from baseline to 8 weeks. We have defined a clinically meaningful decrease in anti-dsDNA antibody titer to be a decrease in titer that is $\geq 35\%$; this is based on serologic data from a previous study comparing the efficacy of prednisone compared to placebo for disease flare prevention in serologically active, clinically stable SLE subjects [39]. For other secondary endpoints, descriptive statistics on continuous

measurements will include means, medians, standard deviations, and ranges, while categorical data will be summarized using frequency counts and percentages.

8. SAFETY MONITORING AND REPORTING (please also reference the Data Safety Monitoring Plan and sections 3.n-3.o of the MOOP)

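### The evaluability cut-off in 5.1 counts t.i.d. doses but calls them pills, and as a fixed count it excludes fully adherent subjects who step down before 23 t.i.d. days

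*Combined protocol and SAP*

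**What the plan says.** Section 5.1 (Design) starts every subject on 750 mg t.i.d. Of duration it says "For both stages of the trial the dosing period is 8 weeks". If t.i.d. dosing is not tolerated, "subjects will be allowed to decrease the dose to twice daily", and no earliest day for this is set. The same section says "Compliance will be monitored by pill count" and requires all evaluable subjects to be at least 80% compliant, which it equates with "≥ 135 of 168 pills".

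Section 3.2 (Drug Description) lists tablets of 250 mg and 625 mg. In the licensed HIV regimen it describes the 750 mg dose as "750 mg (three 250 mg tablets) three times daily". The strength dispensed in this trial is not stated.

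Section 5.4.1 (Study Visits) has "Dispense 30 days of study drug, nelfinavir" on both Day 1 and Day 28, and schedules a pill count on Days 7, 14, 28 and 56. It gives no denominator.

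Section 7.1.1 restates the rule: a subject is evaluable for efficacy if he or she has "complied with at least 80% of the prescribed medication dosing over the entire 56 days of medication administration". Anyone below that is replaced and left out of the efficacy analysis. The rule is introduced as one already given elsewhere in the protocol.

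**The concern.** The cut-off has two faults.

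- **Unit.** The method is a pill count, but 168 is neither the number of tablets prescribed nor the number dispensed. A site that counts tablets has nothing to compare with it.
- **Denominator.** Read as doses, 168 is the full t.i.d. course. The protocol allows fewer doses per day after a step-down but does not say whether the 80% is then taken of 168 or of the subject's own reduced schedule.

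The threshold decides who is counted among the 13 and the 43 in the Simon rules. Stage 1 turns on 3 versus 4 responders among 13, so one reclassified subject could change a decision. As a fixed count, the rule would selectively remove subjects who did not tolerate t.i.d. dosing early on, however well they took the reduced schedule.

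**Working it through.** **Inputs.** 3 doses per day, or 2 after step-down (5.1); 56 days (5.1, 7.1.1); 80% (5.1, 7.1.1); three 250 mg tablets per 750 mg (3.2, inferred for this trial, since 750/625 = 1.2 rules out whole 625 mg tablets); two 30-day supplies (5.4.1).

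**1. The plan's own figure.** 3 × 56 = 168, and 0.80 × 168 = 134.4, rounded up to 135. It reproduces exactly, with one pill taken as one t.i.d. dose.

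**2. The same course in 250 mg tablets.**
- Prescribed: 3 × 3 × 56 = 504.
- 80%: 0.80 × 504 = 403.2, rounded up to 404.
- Dispensed: (30 + 30) × 9 = 540.
- 135 read as tablets: 135/504 = 26.8%, or 135/9 = 15 days of t.i.d. dosing.

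**3. Step-down, with 135 as a fixed dose count.** After d t.i.d. days and b.i.d. for the rest, the most a subject can take is 3d + 2(56 − d) = 112 + d. The condition 112 + d ≥ 135 gives d ≥ 23.

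**4. The two rules side by side.** The third column applies if the denominator in 7.1.1 follows the step-down, and is 0.80 × (112 + d) rounded up. The last column gives the dose totals that are evaluable under 7.1.1 on that reading but not under the fixed count.

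| t.i.d. days (d) | Maximum doses (% of 168) | 80% of own schedule | Adherence needed for 135 | Doses classified differently |
|---|---|---|---|---|
| 0 | 112 (66.7%) | 89.6 → 90 | not reachable | 90–112 |
| 7 | 119 (70.8%) | 95.2 → 96 | not reachable | 96–119 |
| 14 | 126 (75.0%) | 100.8 → 101 | not reachable | 101–126 |
| 22 | 134 (79.8%) | 107.2 → 108 | not reachable | 108–134 |
| 23 | 135 (80.4%) | 108 | 135/135 = 100% | 108–134 |
| 28 | 140 (83.3%) | 112 | 135/140 = 96.4% | 112–134 |
| 42 | 154 (91.7%) | 123.2 → 124 | 135/154 = 87.7% | 124–134 |

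**5. Sensitivity to the visit window.** Section 5.4.1 allows 3 days either side of Day 56. If dosing runs to the visit (an assumption), the condition for T dosing days is 2T + d ≥ 135. This gives d ≥ 29 for T = 53 and d ≥ 17 for T = 59.

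**The case against.** The strongest reply is that nothing is miscalculated. On this view 80% is the operative rule, the count in parentheses merely illustrates it for the default t.i.d. course, and prescribed dosing in 7.1.1 naturally follows a permitted step-down. The two sections would then be one rule, needing only a change of noun. Further, the tablet totals rest on an inferred strength, the Manual of Procedures may define the count, and replacement keeps the evaluable number as planned.

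Much of this is fair. The rounding is right, doses are the likelier intent, and a subject with 26.8% of the course would pass only if a site used the count and ignored both statements of 80%. The manual and the case report forms are not among the documents and may add detail.

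The reply does not remove the problem. Section 5.1 gives the count as an equivalent of 80% for all evaluable subjects, shortly after permitting the step-down, and not as an example. Section 7.1.1 refers back to the earlier rule and does not define its denominator. The sponsor might also intend 80% of the full t.i.d. course as an exposure requirement, and the text supports that reading too. Replacement preserves how many subjects are counted, but not which ones.

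**Conclusion.** The concern holds. The cut-off is a dose count labelled as pills. Taken literally as tablets it contradicts its own 80% (26.8%, assuming 250 mg tablets). Taken as a fixed dose count over 56 days, it makes every subject who steps down before 23 t.i.d. days non-evaluable, even with perfect adherence. The visit window can move that break-even to between 17 and 29 days but does not remove the conflict. If the denominator in 7.1.1 follows the step-down, the two sections disagree over the dose ranges in the table.

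How many subjects this affects cannot be estimated, because the documents give no step-down rate. No change in alpha or power is claimed. It should be fixed because it concerns entry to the primary efficacy count and results are classified subject by subject as each completes Day 56 (7.1).

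**What to change.** Delete the pill figure from 5.1 and state one rule in 5.1 and 7.1.1:

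- Compliance is tablets taken divided by tablets prescribed for that subject over the full planned 56 days, and must be at least 80%. Days after early discontinuation stay in the denominator.
- The denominator follows a permitted step-down. If the sponsor instead means to leave stepped-down subjects out of the efficacy set, that should be a separate, explicit criterion and not the by-product of a pill count.
- Tablets taken are tablets dispensed minus tablets returned. The two 30-day supplies are not the denominator.
- Say how tablets taken after Day 56 but within the visit window are counted.
- Record the date of any step-down.

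A total such as 404 of 504 should appear only as an example for an unmodified t.i.d. course in 250 mg tablets. No dose or step-down rule changes.

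The cost is a short wording change in each of the two sections and a subject-specific calculation. Pill counts are already scheduled, and the step-down date may already be on the case report forms.
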